##### **Primary outcome:**

- Fatal or non-fatal major bleeding (defined as any blood transfusion and/or any hospitalization with associated bleeding) in all three patient groups

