### **8.2 OUTCOMES**

#### **8.2.1 Primary outcomes**

Operational definition of fatal or non-fatal major bleeding is the first new confirmed diagnosis of

- blood transfusion (inpatient or outpatient)  
OR
- bleeding of inpatient (non-DPC hospital)  
OR
- bleeding of inpatient (DPC hospital) with “disease name behind this hospitalization” (“dpcdiseasesegment”=21)

during the follow up period. The ICD-10 diagnosis codes of blood transfusion and bleeding are in [Annex 3](#).

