#### **8.2.2 Secondary outcomes**

Operational definition of composite outcome of stroke/SE/MI/all-cause mortality (inpatient)/major bleeding/major GI bleeding (hospitalization due to GI bleeding)/ICH is the first new confirmed diagnosis of

- Stroke/SE/MI/ Major bleeding (defined as primary outcome)/ICH  
OR
- Major GI bleeding (hospitalization due to GI bleeding)  
OR
- All-cause mortality (inpatient)

during the follow up period. The ICD-10 diagnosis codes of stroke, SE, MI, major bleeding, ICH, major GI bleeding and death are in [Annex 3](#).

Major GI bleeding (hospitalization due to GI bleeding) is the first new confirmed diagnosis of major GI bleeding in inpatient claims from non-DPC hospital or inpatient claims with “disease name behind this hospitalization” (“dpcdiseasesegment”=21) from DPC hospital.

All-cause mortality (inpatient) is:

Proprietary confidential information © 2022 Boehringer Ingelheim International GmbH or one or more of its affiliated companies

- Death of discharge status
  - OR
- Died within 24 hours of admission in FF1 data (discharge summary data)
  - OR
- Confirmed diagnosis of death in inpatient claims.

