### PROCEDURE CODE:

Procedure	Kubun code	Description
Hemodialysis	C102	Home self-peritoneal irrigation guidance management fee
	C102-2	Home hemodialysis frequent time guidance management
	C155	Automated peritoneal irrigation equipment add-on fee
	J038-2	Continuous mild blood filtration
	J038-21	Impaired people add-on fee (continuous mild hemofiltration)
	J038-22	Impaired people add-on fee (continuous mild hemofiltration)
	K635-3	Catheter intraabdominal placement for continuous ambulatory peritoneal dialysis
Joint replacement	K082-21	Artificial joint removal (knee)
	K082-22	Artificial joint removal (foot)
	K082-23	Artificial joint removal (finger)
	K082-31	Artificial joint reimplantation add-on fee (knee)
	K082-32	Artificial joint reimplantation add-on fee (foot)
	K082-33	Artificial joint reimplantation add-on fee (finger)
	K082-4	Total joint replacement of autologous costal bone and cartilage
	K082-5	Total artificial talus replacement
	K082-6	Hip prosthesis sliding surface exchange
	K083	Direct traction using steel codes, and others
Pregnancy	K083-2	Arthrodesis for clubfoot using foot plate and pinch bar
	K890	Tuboplasty (tubo-ovarian transplant, tubal bypass procedure and others)

Proprietary confidential information © 2022 Boehringer Ingelheim International GmbH or one or more of its affiliated companies

	K890-2	Falloposcopic tuboplasty
	K890-3	Laparoscopic salpingoplasty
	K891	Hysterocervicotomy during delivery (including suture)
	K892	Vaginal breech delivery
	K893	Aspiration delivery
	K8941	Outlet/low forceps delivery
	K8942	Middle forceps delivery
	K895	Perineal/vulvar incision and suturing (during delivery)
	K8961	Perineal/vaginal tear suturing (during delivery) (with involvement of the muscular layer)
	K8962	Perineal/vaginal tear suturing (during delivery) (with involvement of the anal)
	K8963	Perineal/vaginal tear suturing (during delivery) (up to vaginal fornix)
	K8964	Suturing of perineal/vaginal tear (associated with rectal tear) (during delivery)
	K897	Endocervical tear suturing (during delivery)
	K8981	Caesarean delivery (emergency cesarean section)
	K8982	Cesarean section (selective cesarean section)
	K8983	Complication add-on fee (hysterotomy)

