# BOEHRINGER INGELHEIM Group of Companies

## Statistical and Epidemiological Analysis Plan (SEAP) for Non-Interventional Studies (NIS)

c38948754-01

Page 22 of 32

Proprietary confidential information © 2022 Boehringer Ingelheim International GmbH or one or more of its affiliated companies

Blood transfusion	K92.0	Haematemesis
	D50	Iron deficiency anaemia
	D50.0	Iron deficiency anaemia secondary to blood loss (chronic)
	D50.1	Sideropenic dysphagia
	D50.8	Other iron deficiency anaemias
	D50.9	Iron deficiency anaemia, unspecified
	D62	Acute posthaemorrhagic anaemia
	D64.9	Anaemia, unspecified
	H35.6	Retinal haemorrhage
	I31.2	Haemopericardium, not elsewhere classified
	I60	Subarachnoid haemorrhage
	I60.0	Subarachnoid haemorrhage from carotid siphon and bifurcation
	I60.1	Subarachnoid haemorrhage from middle cerebral artery
	I60.2	Subarachnoid haemorrhage from anterior communicating artery
	I60.3	Subarachnoid haemorrhage from posterior communicating artery
	I60.4	Subarachnoid haemorrhage from basilar artery
	I60.5	Subarachnoid haemorrhage from vertebral artery
	I60.6	Subarachnoid haemorrhage from other intracranial arteries
	I60.7	Subarachnoid haemorrhage from intracranial artery, unspecified
	I60.8	Other subarachnoid haemorrhage
	I60.9	Subarachnoid haemorrhage, unspecified
Bleeding	I61	Intracerebral haemorrhage
	I61.0	Intracerebral haemorrhage in hemisphere, subcortical
	I61.1	Intracerebral haemorrhage in hemisphere, cortical
	I61.2	Intracerebral haemorrhage in hemisphere, unspecified
	I61.3	Intracerebral haemorrhage in brain stem
	I61.4	Intracerebral haemorrhage in cerebellum
	I61.5	Intracerebral haemorrhage, intraventricular
	I61.6	Intracerebral haemorrhage, multiple localized
	I61.8	Other intracerebral haemorrhage
	I61.9	Intracerebral haemorrhage, unspecified
	K92.2	Gastrointestinal haemorrhage, unspecified
	M25.0	Haemarthrosis
	M25.00	Haemarthrosis, multiple sites
	M25.01	Haemarthrosis, shoulder region
	M25.02	Haemarthrosis, upper arm
	M25.03	Haemarthrosis, forearm
	M25.04	Haemarthrosis, hand
	M25.05	Haemarthrosis, pelvic region and thigh
	M25.06	Haemarthrosis, lower leg

Proprietary confidential information © 2022 Boehringer Ingelheim International GmbH or one or more of its affiliated companies

	M25.07	Haemarthrosis, ankle and foot
	M25.08	Haemarthrosis, other
	M25.09	Haemarthrosis, site unspecified
	N92.0	Excessive and frequent menstruation with regular cycle
	R04	Haemorrhage from respiratory passages
	R04.0	Epistaxis

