# BOEHRINGER INGELHEIM Group of Companies

## Statistical and Epidemiological Analysis Plan (SEAP) for Non-Interventional Studies (NIS)

c38948754-01

Page 24 of 32

Proprietary confidential information © 2022 Boehringer Ingelheim International GmbH or one or more of its affiliated companies

		Prior stroke/transient ischemic attack (TIA)/SE Cerebrovascular disease Myocardial infarction Acute Coronary Syndrome Unstable angina Bleeding history Renal dysfunction Hepatic dysfunction Cancers Peptic ulcer disease Obesity	 1160-0308 Comorbidities.xlsx
4	Co-medications	Anti-platelet drugs	Anti-platelet drugs include aspirin, clopidogrel, ticagrelor and prasugrel. The number of anti-platelet drugs is the number of anti-platelet drugs prescribed on the earliest prescription date before or on the index date during the look back period. Anti-platelet use duration is based on the number of days from the earliest anti-platelet prescription date to the index date.  Receipt codes presented in the following excel file:   1160-0308 Comedication.xlsx
		The number of anti-platelet drugs per prescription	
		Anti-platelet use duration	
		Nonsteroidal anti-inflammatory drugs	
		Gastric secretion inhibitors	
		Statins	
		Heparins	
		Proton pump inhibitor	
		Antihypertensive drugs	
5	Medical procedures	Cardioversion procedures	 Receipt codes presented in the following excel file:   1160-0308 Medical procedure.xlsx
		Ablation procedures	
		Percutaneous Coronary Intervention or Coronary Artery Bypass Grafting	

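### SAP Annex 3 lists no code for a blood transfusion and includes anaemia codes that name no bleeding, so the coded primary outcome is not the one the protocol defines

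*SAP*

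**What the plan says.** Protocol 9.3.2.1 gives the primary outcome as fatal or non-fatal major bleeding, "defined as any blood transfusion and/or any hospitalization with associated bleeding".

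SAP 8.2.1 turns this into the first new confirmed diagnosis in any of three limbs:

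- blood transfusion, in inpatients or outpatients;
- bleeding in an inpatient of a non-DPC hospital;
- bleeding in an inpatient of a DPC hospital, where the diagnosis is flagged as the disease behind the admission (segment 21).

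It then says where the codes are: "The ICD-10 diagnosis codes of blood transfusion and bleeding are in" Annex 3.

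Annex 3 prints K92.0 (haematemesis), then seven anaemia codes, then haemorrhage codes by site. The anaemia codes include D50.1, "Sideropenic dysphagia", and two (D50.9 and D64.9) whose descriptions come down to "anaemia, unspecified".

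SAP 8.2.2 carries the same definition into the net-clinical-benefit composite: "Stroke/SE/MI/ Major bleeding (defined as primary outcome)/ICH".

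**The concern.** A transfusion is a procedure. The SAP looks for it among ICD-10 diagnoses and then lists none that describes one. This creates two errors in opposite directions. Transfusions that the protocol counts are lost when no qualifying listed diagnosis goes with them. Events that the protocol does not count can enter through a diagnosis alone.

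The affected variable is the primary endpoint. It also feeds the secondary composite and, under SAP 7.1, the sample-size calculation that decides whether dabigatran and rivaroxaban are compared. In a safety comparison, false events spread evenly over the groups pull the hazard ratio toward 1 and can hide a real difference in bleeding.

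**Working it through.** **Definition against code list**

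| Element | Protocol 9.3.2.1 | SAP 8.2.1 and Annex 3 |
|---|---|---|
| Transfusion | Any transfusion | An ICD-10 diagnosis; 0 of 52 printed codes describes a transfusion |
| Setting of the transfusion limb | Not restricted | Inpatient or outpatient, so a listed diagnosis suffices without transfusion or admission |
| Bleeding | Hospitalisation with associated bleeding | Inpatient diagnosis from a list that includes non-bleeding anaemia |

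**The seven anaemia codes.** D50.0 (secondary to blood loss) and D62 (posthaemorrhagic) name bleeding and are not at issue. D50, D50.1, D50.8, D50.9 and D64.9 do not.

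**Where the blocks divide.** In the text of Annex 3, the label for blood transfusion stands beside K92.0, and the boundary with the bleeding block is unclear. Both readings fail:

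- If the transfusion block holds only K92.0, an outpatient haematemesis diagnosis with no transfusion and no admission is a major bleed. An inpatient diagnosis of unspecified anaemia is also one. In a DPC hospital it must carry segment 21; in a non-DPC hospital no reason-for-admission condition applies.
- If the anaemia codes belong to the transfusion block, an outpatient anaemia diagnosis is enough.

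No placement of the boundary produces a transfusion code.

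**The SAP's own practice elsewhere.** Annex 2 finds procedures by Kubun code, for example "Catheter intraabdominal placement for continuous ambulatory peritoneal dialysis". Annex 4 says of cardioversion, ablation and coronary revascularisation: "Receipt codes presented in the following excel file". Pregnancy (SAP 7.3) and death (SAP 8.2.2) draw on discharge-summary data. Transfusion is the exception.

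**Validation.** Protocol 9.8 promises validated algorithms where possible. The ENCePP checklist in Protocol Annex 2 answers No on validity of outcome measurement (6.3) and on control of outcome misclassification (10.6). The three references in SAP 13.1 are all statistical.

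**Illustration of size.** No stated figure of the plan is in dispute here. Inputs from Protocol 9.5: a rate of 3 per 100 patient-years, taken as the pooled rate with equal arms, and hazard ratios of 0.66 and 0.74. The false-positive rate f is assumed, and assumed equal in both arms.

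- Warfarin rate = 2 × 3 / (1 + HR); NOAC rate = HR × warfarin rate.
- HR 0.66: warfarin 6/1.66 = 3.614, dabigatran 2.386.
- HR 0.74: warfarin 6/1.74 = 3.448, rivaroxaban 2.552.
- Observed HR = (NOAC rate + f) / (warfarin rate + f).

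| f per 100 PY | True HR 0.66 | False share of warfarin events (0.66 case) | True HR 0.74 |
|---|---|---|---|
| 0.5 | 2.886/4.114 = 0.70 | 0.5/4.114 = 12% | 3.052/3.948 = 0.77 |
| 1 | 3.386/4.614 = 0.73 | 1/4.614 = 22% | 3.552/4.448 = 0.80 |
| 2 | 4.386/5.614 = 0.78 | 2/5.614 = 36% | 4.552/5.448 = 0.84 |

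If the rate of 3 already contains the false events, the true pooled rate is 3 − f, and 0.66 becomes 0.71, 0.76 or 0.87.

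**The case against.** The best defence has four parts.

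- **The table is unreliable.** Row labels are displaced elsewhere in the SAP's annexes too. K92.0 stands first and out of order, and the remaining codes run in sequence from D50 to R58, so the break probably falls right after K92.0. The outpatient route would then admit only haematemesis, which is a bleed, and anaemia would need an inpatient diagnosis. This stands as the likelier reading and narrows the anaemia route. It does not supply a transfusion code, and it still counts non-bleeding anaemia.
- **The protocol itself says outcomes are recorded in ICD-10 (9.3.2).** True, and that sentence sits awkwardly with the definition in 9.3.2.1. The SAP nevertheless leaves ICD-10 wherever a variable needs it, including for inpatient death.
- **Few events may be lost.** A transfused inpatient who meets an inpatient bleeding limb is still captured. This stands: only transfusions without a qualifying diagnosis are missed, and their number is unknown. If the same proportion is missed in each group, the event count falls but the hazard ratio changes little.
- **Anaemia as a reason for admission may be meant as a proxy for occult bleeding.** That is possible, but the SAP gives no such rationale. Checklist item 7.3 does answer Yes on information bias, citing Protocol 9.8, but that section cites no validated algorithm for this outcome.

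The hazard ratios above rest on assumed rates. The mismatch itself does not depend on them.

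**Conclusion.** The concern holds and should be fixed before analysis. Read literally, the SAP does not implement the protocol's primary outcome: it has no means of recognising a transfusion, and it accepts diagnoses that are neither a transfusion nor bleeding. This follows from the printed text under either reading of the table.

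The effect on the results cannot be estimated from the documents. The range of 0.70 to 0.78 for a true 0.66, and 0.77 to 0.84 for a true 0.74, assumes false-positive rates of 0.5 to 2 per 100 patient-years, equal across groups and added to the planning rate. Unequal rates could bias the hazard ratio in either direction. No loss of power is claimed.

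**What to change.** In SAP 8.2.1 and Annex 3:

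1. Identify the transfusion limb by transfusion procedure codes (Kubun or receipt) and blood-product codes, and take diagnosis codes out of it. State whether the protocol's condition of associated bleeding applies to transfusions as well as to admissions. Reconcile the general ICD-10 sentence in Protocol 9.3.2 with this.
2. Treat K92.0 as a bleeding diagnosis under the two inpatient limbs.
3. Remove D50, D50.1, D50.8, D50.9 and D64.9 from the primary definition. Alternatively, justify them and report a sensitivity analysis without them.
4. Print Annex 3 with a clear boundary between the transfusion and bleeding blocks.

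The cost is a revised code list and re-derivation of one variable in existing data; the composite then follows. The sponsor should confirm that transfusion and blood-product records can be extracted. The documents describe insurance claims data and use procedure codes for other items, but do not mention transfusion records. Event counts may differ from those assumed in planning.

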#### **8.2.2 Secondary outcomes**

Operational definition of composite outcome of stroke/SE/MI/all-cause mortality (inpatient)/major bleeding/major GI bleeding (hospitalization due to GI bleeding)/ICH is the first new confirmed diagnosis of

- Stroke/SE/MI/ Major bleeding (defined as primary outcome)/ICH  
OR
- Major GI bleeding (hospitalization due to GI bleeding)  
OR
- All-cause mortality (inpatient)

during the follow up period. The ICD-10 diagnosis codes of stroke, SE, MI, major bleeding, ICH, major GI bleeding and death are in [Annex 3](#).

Major GI bleeding (hospitalization due to GI bleeding) is the first new confirmed diagnosis of major GI bleeding in inpatient claims from non-DPC hospital or inpatient claims with “disease name behind this hospitalization” (“dpcdiseasesegment”=21) from DPC hospital.

All-cause mortality (inpatient) is:

Proprietary confidential information © 2022 Boehringer Ingelheim International GmbH or one or more of its affiliated companies

- Death of discharge status
  - OR
- Died within 24 hours of admission in FF1 data (discharge summary data)
  - OR
- Confirmed diagnosis of death in inpatient claims.

### **8.3 COVARIATES**

Please check section 9.3.3. of the study protocol. List of covariates and operational definitions are added to [Annex 4](#).

The HAS-BLED score is calculated as the total points of the following elements (1 point per element) during the baseline period including the index date.

- Confirmed diagnosis of hypertension
- Dialysis-dependent kidney disease including confirmed diagnosis of hepatic dysfunction or confirmed diagnosis of renal dysfunction or on hemodialysis treatment
  - OR
- Confirmed diagnosis of cirrhosis
  - OR
- Renal transplant
  - OR
- Serum creatinine > 200 m mol/L
  - OR
- ALP > 3x upper limit (1050 IU/L) or ALT > 3x upper limit (132 IU/L) or AST > 3x upper limit (114 IU/L)
  - OR
- Bilirubin > 2x upper limit (2.4 mg/dL)
- Confirmed diagnosis of stroke
- Confirmed diagnosis of bleeding history
- Age calculated as of index date > 65 years old
- Confirmed diagnosis of excessive alcohol use
  - OR
- on treatment of excessive alcohol use
  - OR
- on antiplatelet drugs or non-steroidal anti-inflammatory drug

The CHA2DS2-VASc score is calculated as the total points of the following elements during the baseline period including the index date.

- Confirmed diagnosis of congestive heart failure (1 point)
- Hypertension (1 point) including confirmed diagnosis of hypertension or on any anti-hypertensive medications
- Age calculated as of index date  $\geq$  75 years old (2 points)

---

Proprietary confidential information © 2022 Boehringer Ingelheim International GmbH or one or more of its affiliated companies

- Diabetes Mellitus (1 point) including confirmed diagnosis of diabetes mellitus or on any anti-hyperglycemia agents or on any insulin treatment
- Confirmed diagnosis of stroke (2 points)
- Vascular disease including confirmed diagnoses of MI or peripheral arterial disorder (1 point)
- Age between 65 and 74 (1 point)
- Female (1 point)

The code used to define the elements of HAS-BLED score and CHA2DS2-VASc score are in [Annex 4](#).

## **9. DATA SOURCES**

Please check section 9.4 of the study protocol.

## **10. DATA MANAGEMENT AND SOFTWARE/TOOLS**

Data is stored using the secured Instant Health Data (IHD) platform (<https://www.bhei.com/product>). The database is accessed through a user and password system. All study details are addressed either in the protocol, SEAP, or DMRP.

### **10.1 SOFTWARE/TOOLS**

The cohort selection, exposure, outcomes, and covariates derivation will be conducted in IHD platform and the data analysis will be run in BI internal server using SAS software 9.4 (SAS Institute, Inc., Cary, NC) or R Studio 3.5.2.

### **10.2 HANDLING OF MISSING VALUES**

The absence of a code for a condition will be interpreted as an absence of the event. If a study variable is totally missing from a database, it is excluded from the analysis of the pooled data.

If a variable is missing for only some of the patients a missing data category will be added and utilized in the analysis.

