**Comorbidities (has at least 1 diagnosis before or on the index date during the look-back period)**

- Heart failure (yes/no)
- Peripheral arterial disorder (yes/no)
- Hypertension (yes/no)
- Diabetes (yes/no)
- Prior stroke/transient ischemic attack (TIA)/SE (yes/no)
- Cerebrovascular disease (yes/no)
- Myocardial infarction (yes/no)
- Acute Coronary Syndrome (yes/no)
- Unstable angina (yes/no)
- Bleeding history (yes/no)
- Renal dysfunction (yes/no)
- Hepatic dysfunction (yes/no)
- Cancers (yes/no)
- Peptic ulcer disease (yes/no)
- Obesity (yes/no)

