## **9.9 LIMITATIONS OF THE RESEARCH METHODS**

This is a non-interventional study based on existing data. The data do not include vital signs or laboratory test results (e.g. blood pressure, international normalized ratio values, renal function parameters). Therefore, the study may be subject to potential residual confounding due to the absence of certain key data.

Further, the [REDACTED] database contains around 23% of emergency care hospitals in Japan, which does not form a fully closed healthcare system and therefore could lead to information bias.

Additionally, the mortality is only known for hospitalized patients during hospitalization, thus resulting in inaccurate estimates of the mortality rate.

Due to the above reasons, the study results might not be generalizable to the entire AF patient population in Japan.

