### **11.1 MAIN ANALYSIS**

During the first step of the comparative analysis, the baseline characteristics of the individual NOAC groups will be balanced with the warfarin group to account for potential confounding effects through an inverse probability of treatment weighting (IPTW) method. A multinomial logistic regression model will be used to estimate the generalized propensity score (GPS). The treatment membership (warfarin, dabigatran and rivaroxaban) is the dependent variable and all the covariate variables listed in [Annex 4](#) except for “Anti-platelet drugs” and “The number of anti-platelet drugs per prescription” are independent variables in the multinomial logistic regression model, as the two variables can be fully derived from the variable “Anti-platelet use duration”. For each patient, we will obtain the estimated GPS vector with components of the probabilities of receiving each treatment (warfarin, dabigatran and rivaroxaban) through the multinomial logistic regression model.

The stabilized IPTW (s-IPTW) will be used to deal with the inflation of type I error and extremely large weight when using regular IPTW. The s-IPTW is calculated as

$$w_i = \frac{\Pr(T = k)}{\Pr(T = k|X = x_i)}$$

for the  $i$ th patient, where  $T$  is the treatment membership and  $x_i$  is the covariates of this patient. The denominator is the  $k$ th component of GPS vector of the  $i$ th patient who was actually in treatment group  $k$  and the numerator is the marginal probability of receiving treatment  $k$  [\[R22-1420\]](#).

The GPS distributions (density curves, boxplots) of each treatment will be used to examine GPS overlap between the treatment groups. Patients outside of the common support or overlap area for any component of the GPS vector are removed from the analysis. The area of common support is formed by defining boundaries for each component  $k$ ,  $k = 1, 2, 3$  of the GPS vector [\[R22-1419\]](#):

$$\Pr(T = k|x)^{low} = \max[\min(\Pr(T = k|x, T = 1)), \min(\Pr(T = k|x, T = 2)), \min(\Pr(T = k|x, T = 3))]$$

$$\Pr(T = k|x)^{high} = \min[\max(\Pr(T = k|x, T = 1)), \max(\Pr(T = k|x, T = 2)), \max(\Pr(T = k|x, T = 3))]$$

[figure not shown]
The distributions of s-IPTW for each treatment group will be examined, the mean s-IPTW is expected to be close to 1. Weight truncation based on the distributions of s-IPTW will be applied if there are extremely high s-IPTW.

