#### ANNEX 4. STUDY COVARIATES

N	Category	Variables	Definition
1	Demographic characteristics	Age	- By year (calculated on index date)
		Gender	- Male, Female
2	Ischemic and hematologic characteristics	CHA2DS2-VASc score	Codes used to define elements of CHA2DS2-VASc score in the following excel file:   11600308 CHA2DS2_VASc.xlsx
		HAS-BLED score	Codes used to define elements of HAS- BLED score in the following excel file:   1160-0308 HASBLED.xlsx
3	Comorbidities	Heart failure	ICD-10 diagnosis codes presented in the following excel file:
		Peripheral arterial disorder	
		Hypertension	
		Diabetes	

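### Hospital use in the look-back year is neither in the propensity weights nor in the balance check, so comparability of the drug groups on it is not assured

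*SAP*

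**What the plan says.** **Model.** SAP 11.1 fits a multinomial propensity model in which treatment membership "is the dependent variable and all the covariate variables listed in" Annex 4, apart from two antiplatelet items, are the predictors. Annex 4 covers age and gender, two risk scores under "Ischemic and hematologic characteristics", 15 comorbidities, co-medications and three procedure items, the last being "Percutaneous Coronary Intervention or Coronary Artery Bypass Grafting". Protocol 9.3.3 has the same categories. Neither list has a count of admissions, inpatient days or visits.

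**Coding.** Protocol 9.3.3 defines the conditions as "Comorbidities (has at least 1 diagnosis before or on the index date during the look-back period", so one code is enough. SAP 10.2 adds: "The absence of a code for a condition will be interpreted as an absence of the event".

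**Database.** Protocol 9.9 says that it "does not form a fully closed healthcare system and therefore could lead to information bias". Entry (protocol 9.2) needs 365 days of proxy enrolment, counted from the first encounter, and sets no minimum amount of contact.

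**Outcomes.** In SAP 8.2.1, major bleeding is "blood transfusion (inpatient or outpatient"), or "bleeding of inpatient (non-DPC hospital"), or inpatient bleeding in a DPC hospital that carries a marker tying the diagnosis to that admission. In SAP 8.2.2, major GI bleeding and mortality are inpatient only. The text gives no care setting for stroke, systemic embolism, MI or ICH.

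**Balance.** Balance is judged by an ASD below 0.1. The outcome model is adjusted further only for covariates found out of balance (SAP 11.1).

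**The concern.** Amount of hospital contact can act at four points.

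- **Baseline coding.** A patient seen rarely has fewer chances to collect a code and looks healthier than one seen often.
- **Outcome risk.** Prior admission plausibly marks a higher risk of later admission.
- **Outcome capture.** In an open system, a bleed treated at another hospital is not seen. In non-DPC hospitals an inpatient bleeding code counts without having to be the reason for admission, so more inpatient time gives more chance of being counted.
- **Observed time.** Follow-up ends at the last encounter at the latest.

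If the drug groups differ in hospital use after weighting, part of that difference would be read as a drug effect on the primary and composite outcomes. The plan's safeguards would not reveal it. The ASD tables and the fallback Cox adjustment work only on listed covariates, and 1:1 matching would not help if it uses the same list.

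**Working it through.** **Plan's own figure.** The plan gives no figure for hospital use, so nothing can be reproduced on the point itself. The planned effect, HR 0.66 for dabigatran against warfarin (protocol 9.5), serves as reference. By Schoenfeld's formula (80% power, 1:1 allocation, two-sided 5% assumed) it needs 182 events. At 3 per 100 patient-years over 1 year that is 182 / 0.03 = 6067 patients, against 6050 stated.

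**Formula.** For one binary factor left out of the model, with prevalence pN in the NOAC group and pW in the warfarin group, and rate ratio RR for the outcome:

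bias factor = [1 + pN(RR − 1)] / [1 + pW(RR − 1)]; observed HR = true HR × bias factor.

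All values of pN, pW and RR below are assumptions. None is in the documents.

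**Case A: crude gap, nothing absorbed by other covariates.** pN 0.30-0.40, pW 0.45-0.60, RR 1.5-2.5. The factor rises with pN and falls with pW and RR, so two corners give the range.

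- Smallest: (1 + 0.30 × 1.5) / (1 + 0.60 × 1.5) = 1.45 / 1.90 = 0.763; 0.66 × 0.763 = 0.50.
- Largest: (1 + 0.40 × 0.5) / (1 + 0.45 × 0.5) = 1.20 / 1.225 = 0.980; 0.66 × 0.980 = 0.65.

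The first corner is a very large imbalance: ASD = 0.30 / √[(0.21 + 0.24) / 2] = 0.63.

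**Case B: small residual gap after weighting.** pN 0.35, pW 0.40, RR 1.25-3. ASD = 0.05 / √[(0.2275 + 0.24) / 2] = 0.10, which is the plan's own threshold.

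- RR 1.25: 1.0875 / 1.10 = 0.989; 0.66 reads 0.65.
- RR 3: 1.70 / 1.80 = 0.944; 0.66 reads 0.62.

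**Reversed direction.** With NOAC 40% and warfarin 35%, the factors invert to 1 / 0.989 = 1.01 and 1 / 0.944 = 1.06.

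**Effect on false positives.** Take the expected counts (17000 warfarin; 4000 dabigatran or 11000 rivaroxaban), 3 per 100 patient-years and 1 year. Events are 0.03 × 21000 = 630 and 0.03 × 28000 = 840. With SE = 1 / √[events × a(1 − a)], where a is the NOAC share, the SEs are 0.101 and 0.071. An assumed factor of 0.95 shifts log HR by 0.051, which is 0.51 and 0.73 standard errors. The two-sided 5% error becomes about 8% and 11%. These are unweighted counts, so they are approximate.

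**The case against.** The strongest case against has five parts.

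1. **No evidence of imbalance.** Nothing in the documents gives hospital use by drug. A reader might infer that warfarin starters use the hospital more and that the study is therefore tilted towards the NOACs. The documents do not support this; the direction could be the opposite. This objection stands in full.
2. **Outcomes.** A reader might infer that most outcomes are admissions. Of the seven composite components, only GI bleeding and mortality are wholly inpatient, and major bleeding largely so. Transfusion may be outpatient, and four components have no stated setting. This stands.
3. **Partial proxies.** Heparins, PCI/CABG, ablation, cardioversion, ACS and MI often imply hospital care and are in the model. Not every covariate is a yes/no flag: antiplatelet duration has seven levels. SAP 8.3 also puts laboratory values into HAS-BLED, although protocol 9.9 says that the data hold none. These items reduce the problem, but they mark particular events or conditions rather than the amount of contact.
4. **Follow-up rules.** Patients are censored at a 45-day refill gap, at a switch or at the last encounter, so those at risk are still in contact with the database. This limits differential capture but does not exclude it, since a bleed can be treated elsewhere while refills continue.
5. **Already acknowledged.** Protocol 9.9 names information bias and residual confounding, and protocol 9.7.2 and SAP 11.2 are redacted, so a related sensitivity analysis may exist. The Annex 4 list that governs the main model is readable, however, and has no such variable.

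**Conclusion.** The omission is verifiable: prior-year hospital use is neither balanced directly nor checked, so comparability on it is not assured. It is not shown that the groups differ on it, nor that the hazard ratios will be biased.

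The size rests wholly on assumed inputs. Case A multiplies the HR by 0.76-0.98, but it ignores everything that the listed covariates absorb. Case B, a residual gap at the balance threshold, gives 0.94-0.99.

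A single factor is unlikely to explain the whole planned effect. The E-value, 1/HR + √[(1/HR)(1/HR − 1)], is 2.40 for HR 0.66 and 2.04 for the rivaroxaban assumption of 0.74. A modest shift is possible, and with samples of this size it can change what a confidence interval excludes. The point is worth acting on because the remedy is cheap and specific, not because the plan contains an error.

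**What to change.** Add three variables to protocol 9.3.3 and SAP Annex 4, measured over the 365-day look-back: number of admissions, inpatient days and outpatient encounters. Through Annex 4 they enter the propensity model; add them to the Table 2 shells for the ASD, so that they are also open to the fallback Cox adjustment. The protocol list needs the change too, because protocol 9.7.1 uses all covariates.

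State the functional form before outcomes are analysed (for example, admissions as 0, 1, 2 or more), and state how an admission already open on the index date is counted.

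If the sponsor prefers not to extend the model, the minimum is to report the ASD of these counts before and after weighting, with a quantitative bias analysis if any exceeds 0.1.

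The cost is a few variables derived from the encounter records that already define the enrolment proxy, a matching edit in both documents, slightly more variable weights and possibly a few more patients outside the common support.
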